## **6.9 ACCOUNTABILITY AND COMPLIANCE OF STUDY MEDICATION**

The Investigator or pharmacist/designee may dispense study medication(s) only to patients enrolled in the study. Individual patient accountability records must be kept by the site staff. The patient number, the date, batch number/wallet number, and quantity of study medication used or returned by the patient will be recorded on the appropriate accountability forms by the site staff. These records and the inventory of study medication on site will be verified by the study monitor for accuracy and completeness on an ongoing basis throughout the study. Unused drug supplies will be disposed of as instructed in the Study Pharmacy Manual.

Treatment compliance will be assessed at all visits during the study. It will be based on

accountability records and an inventory of used/unused supplies. Study medications compliance may be enhanced with regular telephone calls and other reminders.

At the end of the study, the monitor will conduct a final drug reconciliation for all patients and the study site overall. All records of study medication receipt, accountability records and drug disposition records will be examined and reconciled by the study monitor. Further details will be provided in the Study Pharmacy Manual.

## **6.10 PRIOR AND CONCOMITANT THERAPY**

### **6.10.1 General Guidelines**

All prior treatments received by the patient, e.g. general use since diagnosis (list of prior medications for acromegaly any time in the past), medications for acromegaly within the last year (including the last dose of SRL injection) and medications for other conditions – within the last 12 weeks of the initial Screening visit will be recorded on the patient's eCRF including the treatment's name, indication and the start and stop dates.

Any medications (including prescription, over-the-counter, herbal supplements and health store products) to be taken during the study must be approved by the Investigator and recorded on the concomitant medication eCRF page.

All concomitant medications taken by the patient must be recorded on the eCRF, along with the indication and start and stop dates as well as daily dose.

### **6.10.2 Prohibited Prior Medications or Therapies**

The following are prohibited prior medications or therapies:

- Treatment with pegvisomant within 24 weeks before the first screening visit
- Treatment with dopamine agonists within 12 weeks before the first screening visit
- Treatment with pasireotide within 24 weeks before the first screening visit
- Treatment with long-acting SRLs at a dosing frequency different than once monthly except for lanreotide 120 mg every six or eight weeks
- Conventional or stereotactic radiotherapy any time in the past
- New treatment with estrogens and/or selective estrogen receptor modulators (SERMs)

(stable regimen of estrogens and/or SERMs will be permitted. Women who are treated with oral contraceptives for 21 days or who are treated with active (hormone containing) pills for 21 days and with non-active pills (non-hormone containing), during the monthly period should make all efforts to schedule all their clinical visits during the 21 days when active hormonal contraception is administered and preferably on the same week pre/post the monthly period).

### **6.10.3 Allowed Medications**

Other than the investigational medicinal drugs, concomitant medications allowed to be used in this study are those used at screening to control existing medical condition, and/or those taken during the study to treat possible AEs. Per the Investigator discretion, new/worsening acromegaly clinical

signs or symptoms could be medically treated (e.g. with analgesics, antidiabetic or antihypertensive medications) while the patient remains in the study.

Concomitant administration of octreotide capsules and thyroid hormone replacement therapy (HRT) is permitted on an empty stomach after an overnight fast or two hours after breakfast. PPIs and H2 blockers are advised to be taken at least 30-60 minutes prior to meals and at least 1 hour after octreotide capsule administration. Anti-acid is advised to be taken with food or just prior to meals. Timing of octreotide capsules intake in patients taking anti-diabetic medications should be discussed with the study investigator/study nurse.

Loperamide is allowed to treat GI symptoms.

Acute steroid use should be documented on the appropriate eCRF page.

All concomitant medications used to treat AEs will be recorded in the patient's medical file and on the appropriate eCRF page.

If intake of a new systemic prescription drug should become necessary for any reason during the course of the study, the patient is required to inform the Investigator immediately, who will record the drug, the dose and the time of administration in the patient's eCRF.

#### **6.10.4 Prohibited Concomitant Medication**

Women taking oral contraception containing levonorgestrel are advised to switch to another oral contraceptive or barrier method.

Investigational therapy for the treatment of acromegaly are prohibited during the course of the study.

Parenteral SRLs or dopamine agonists, GH antagonists are prohibited while the patient is treated with study medication (octreotide capsules/placebo).

## **7 SAFETY AND PHARMACOVIGILANCE**

### **7.1 ADVERSE EVENT**

The FDA defines an AE as “Adverse event means any untoward medical occurrence associated with the use of a drug in humans, whether or not considered drug related” ([US Department of Health and Human Services Food and Drug Administration December 2012](#)).

An AE (also referred to as an adverse experience) can therefore be any unfavorable and unintended sign (e.g., an abnormal laboratory finding), symptom, or disease temporally associated with the use of a drug, without any judgment about causality or seriousness. An AE can arise from any use of the drug (e.g., off-label use, use in combination with another drug) and from any route of administration, formulation, or dose, including an overdose.

An abnormal result of diagnostic procedures including abnormal laboratory findings will be considered an AE if it fulfills one or more of the following:

- Results in patient's withdrawal by the Investigator
- Is associated with clinical signs or symptoms
- Results in change in study medication schedule or in concomitant medication

- Is considered by the Investigator to be of clinical significance (a laboratory abnormality that is not clinically significant will not be considered an AE)

A new condition or the worsening of a pre-existing condition will be considered an AE.

An adverse reaction means any AE caused by a drug. Adverse reactions are a subset of all suspected adverse reactions for which there is reason to conclude that the drug caused the event.

Suspected adverse reaction is “any AE for which there is a reasonable possibility that the drug caused the adverse event.”

AEs do not include the following:

- Stable or intermittent chronic conditions (such as myopia requiring eyeglasses) that are present prior to study entry and do not worsen during the study.
- Medical or surgical procedures (e.g., surgery, endoscopy, tooth extraction, transfusion). The condition that leads to the procedure is an AE if not present at baseline.
- Overdose of either study medication or concomitant medication without any signs or symptoms unless the patient is hospitalized for observation.
- Hospitalization for elective surgery planned prior to study (situation where an untoward medical occurrence has not occurred).
- Pregnancy will not be considered an AE, but if occurs, will be reported on pregnancy form.

AEs will be assessed at all study visits throughout the study from informed consent signing. AEs reported prior to dosing on Baseline Day will be captured and considered non-treatment emergent AEs. Treatment Emergent AEs (TEAEs) will be considered all AEs that occurred from Baseline (following study medication administration) to end of core study (i.e. end of DPC period). AEs reported after termination/completion of the core study, during the Follow-up period will be reported separately. AEs reported during the OLE period will be reported separately and together with the core study. The final safety analysis will be detailed in the Statistical Analysis Plan (SAP). The date and time of each AE occurrence will be recorded.

All AEs, whether observed by the Investigator or designee or volunteered by the patient, should be recorded individually on an AE eCRF page with the following information: the specific event or condition, whether the event was present pre-study (and if so, should be captured in the medical history eCRF page), the dates and times (using the 24 hour clock, where midnight is 00:00 and noon is 12:00) of occurrence, duration, severity, relationship to study medication, specific countermeasures, outcome, and whether considered non-serious or serious, drug-related or not. AEs will be recorded from the time a patient has signed the informed consent form (ICF) and throughout the study, including the Core study, Follow-up and OLE period. Severity of the AE will be assessed by the Investigator in accordance with the definitions below. An SAE must fulfill the requirements listed in the [Section 7.2](#).

Three definitions only should be used by the investigating physician to describe the severity of the AE ([Table 1](#)). Only one severity (the worst severity) definition should be used for each AE (e.g., "mild/moderate" is not acceptable).

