#### **7.1.1 Adverse Events of Special Interest**

New or worsening acromegaly signs and/or symptoms will be recorded as adverse events of special interest (AESI) and are headache, fatigue, perspiration, soft tissue swelling, arthralgia, dysglycemia or hypertension or other signs that in view of the Investigator are related to acromegaly.

Worsening of symptoms will be any new sign/symptom or shift in severity (e.g. mild to moderate or moderate to severe). Severity will be defined according to [Table 1](#).

Worsening of dysglycemia is a shift in the severity criteria as defined in common terminology criteria for adverse events (CTCAE) v4.03 and shown in [Table 3](#).

Worsening of hypertension is defined as a shift in severity as defined in CTCAE v4.03 and shown in [Table 4](#).

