### 6.9.2.1 DPC period

All AEs that occur after randomization (i.e., date of onset is on or after the date of randomization) and on or before the end of treatment (last dose of blinded study drug) in the DPC period will be considered Treatment Emergent Adverse Events (TEAEs) for the purpose of reporting in the DPC period, and will be summarized using frequency counts and percentages. Summaries will be presented by final dose group and treatment group (i.e., octreotide 40, 60, 80, overall and placebo) and overall for the safety set.

If the day of onset of an AE is missing, then if the month and year of an onset date are on or after the date of randomization, the following rules will be applied:

- If month/year of the onset date is on or after the month/year of randomization, the AE will be considered treatment emergent;
- If month/year of the onset date is equal to the month/year of randomization, and the end date is present, the end date will be used to determine when the AE started. If the end date is on or after randomization, the AE will be considered treatment emergent; otherwise, if the AE stopped before randomization, then it will not be considered treatment emergent;
- If month/year of the onset date is equal to the month/year of randomization, and the end date is a partial date, the AE will be considered treatment emergent;
- If, despite implementing the above conventions, the onset date of the AE cannot be placed before, on, or after randomization, then the event will be considered treatment emergent.

Summaries of TEAEs will be presented using the MedDRA level hierarchy (system organ class, high level group term, high level term, and preferred term) as follows:

- Overall (i.e., regardless of intensity or relationship to treatment)
- By intensity grade (mild, moderate, severe)
- By relationship to study medication (potential relationship to study treatment or unlikely/no relationship to study treatment) according to the mapping scheme below:
  - Related: will include all AEs with a relationship rating of “related” or “possibly related”
  - Not related: will include all AEs with a relationship rating of “Not related”
- Unless otherwise specified, at each level of patient summarization in reporting the incidence of the AEs, a subject will be counted once if the subject reported one or more events. If more than one occurrence of an event is reported, the event of the worst intensity or the worst-case relationship assessment will be summarized.

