#### **6.9.2.2 OLE**

AEs will be considered treatment emergent for the purpose of reporting in the OLE if they meet any of the following criteria:

- AE onset date is after the end of treatment in the DPC period (i.e., date of onset greater than the end of treatment date in the DPC period)
- AE is ongoing, and the severity worsens during the OLE (i.e., date of severity worsening is greater than the end of treatment date in the DPC period)

All summaries will be presented by final dose group (i.e., 40, 60 or 80) and overall for the OLE set.

If the day of onset of an AE is missing, then if the month and year of an onset date are on or after the date of randomization, the following rules will be applied:

- If month/year of the onset date is on or after the month/year of the end of treatment date in the DPC period, the AE will be considered treatment emergent;
- If month/year of the onset date is equal to the month/year of the end of treatment date in the DPC period, and the end date is present, the end date will be used to determine when the AE started. If the end date is on or after the end of treatment date in the DPC period, the AE will be considered treatment emergent; otherwise, if the AE stopped before randomization, then it will not be considered treatment emergent;
- If month/year of the onset date is equal to the month/year of the end of treatment date in the DPC period, and the end date is a partial date, the AE will be considered treatment emergent;
- If, despite implementing the above conventions, the onset date of the AE cannot be placed before, on, or after the end of treatment date in the DPC period, then the event will be considered treatment emergent.

Summaries of TEAEs will be presented using the MedDRA level hierarchy (system organ class, high level group term, high level term, and preferred term) as follows:

Overall (i.e., regardless of intensity or relationship to treatment)

By intensity grade (mild, moderate, severe)

By relationship to study medication (potential relationship to study treatment or unlikely/no relationship to study treatment) according to the mapping scheme below:

Related: will include all AEs with a relationship rating of “related” or “possibly related”

Not related: will include all AEs with a relationship rating of “Not related”

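### The AE record holds one worst severity and no listed date of change, but the open-label treatment-emergent rule and the period-limited safety tables need to know when a grade rose

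*Protocol*

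**What the plan says.** Protocol 7.1 asks for one AE page per event. After the event term, whether it was present before the study, and dates and times, the list continues: "of occurrence, duration, severity, relationship to study medication, specific countermeasures, outcome, and whether considered non-serious or serious, drug-related or not". The next paragraph adds that "Only one severity (the worst severity) definition should be used for each AE" and gives a combined mild-to-moderate entry as an example of what is not accepted.

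Two analysis rules use these data.

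- **DPC period.** SAP 6.9.2.1 assigns events by onset: "All AEs that occur after randomization (i.e., date of onset is on or after the date of randomization", and no later than the last blinded dose. These events are then tabulated by intensity. SAP 6.9 restricts DPC safety analyses to data from that period and excludes anything gathered after the patient stopped study drug. Protocol 8.4.8 states the first restriction but not the second.
- **OLE.** An AE counts if its onset is after DPC end of treatment. It also counts under a second criterion: "AE is ongoing, and the severity worsens during the OLE (i.e., date of severity worsening is greater than the end of treatment date". The cut-off meant there is the DPC one. Protocol 8.4.8.1 has the same rule.

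Core database lock follows the last patient's completion of the DPC period (Protocol 3, SAP 3). Under Appendix A, the Week 36 visit is also the first OLE visit.

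**The concern.** The second OLE criterion treats an event that continues past the end of DPC treatment and then gets worse as the same AE, and it decides the matter on the date of the worsening. The collection rule keeps the highest grade and does not mention when it was reached. An analyst given an onset date, a stop date and one worst grade cannot evaluate the criterion. The same record cannot show which grade applied at the end of DPC treatment.

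Two things are at stake. First, a worsening on open-label capsules may be absent from the OLE tables, which support the long-term safety objective. Second, the DPC intensity table may show a grade reached later. For a patient randomized to placebo, that would put a worsening on open-label octreotide in the placebo column and blur the placebo-controlled safety comparison.

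**Working it through.** The documents give no figure on this point, so the check is to follow one event through the written rules.

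**Inputs**

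1. Severity per AE: one, the worst (Protocol 7.1).
2. Date of severity change: not among the items listed in Protocol 7.1.
3. DPC assignment: by onset date, from randomization to last blinded dose (SAP 6.9.2.1).
4. OLE assignment: onset after DPC end of treatment, or an ongoing AE with a later dated worsening (SAP 6.9.2.2).
5. DPC tables: DPC-period data only, before study drug was stopped (SAP 6.9).
6. Core lock: after the last patient finishes DPC, when earlier patients may already be on open-label capsules.

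**Event traced:** mild at onset in the DPC period, still present at Week 36, severe in the OLE.

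| How the site records the worsening | DPC table | OLE table |
|---|---|---|
| (a) Same record, grade overwritten before core lock, no date | Severe, under the randomized arm | Second criterion cannot be evaluated; event can be missed |
| (b) Same record, updated after core lock or only in the OLE database, no date | Mild, correct | Second criterion still lacks its date; event can be missed |
| (c) New record with its own onset date | Mild, correct | Severe, caught by the first criterion |

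The OLE omission can arise under (a) and (b). The DPC over-grading arises only under (a), where it breaches input 5. Which practice applies is not stated for an AE that began on study.

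Two further readings bear on this.

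- If every worsening opened a new record, its onset would fall after DPC treatment and the first OLE criterion would catch it. The second criterion would then be redundant. Its presence suggests that the authors expected one record to run across the boundary.
- The partial-date rules in SAP 6.9.2.2 deal with an incomplete onset date. None covers a missing date of worsening, so there is no fallback.

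**The same gap inside the core study.** Patients who stop study drug are followed to Week 36, some on injectable rescue (Protocol 4.6.1 and 5.2.3). Take an AE that begins on study drug and worsens after the last dose. Its onset makes it a DPC treatment-emergent event. Its single grade is the later one, and nothing listed shows that the grade was reached off drug. SAP 6.9.3 to 6.9.6 repeat the off-drug exclusion for laboratory, vital-sign, ECG and ultrasound data, which carry visit dates. SAP 6.9.2 does not say how to apply it to an AE grade. Its only rule on intensity is "If more than one occurrence of an event is reported, the event of the worst intensity or the worst-case relationship assessment will be summarized", with no time limit.

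**Size of one error.** About 50 patients at 1:1 gives 50 / 2 = 25 per arm, and 1 / 25 = 4%. One wrongly graded patient moves an arm's severe-AE rate by 4 percentage points.

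**The case against.** The strongest reply is that the plan already has what it needs.

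- Protocol 7.1 counts the worsening of a pre-existing condition as an AE, and Protocol 5.8.1 has exacerbations of an existing condition recorded as AEs. On that reading each worsening has its own onset date, which is practice (c).
- The one-severity sentence, judged by its example, mainly bars combined grades. It does not forbid a second record.
- DPC tables are confined to DPC data, and data after Week 36 go to the OLE database.
- The eCRF and its completion guideline are not among the documents. The OLE rule names a date of worsening, so its authors presumably expected to have one.

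Much of this stands. A reader might infer that a worsened event is bound to be charged to the DPC arm at its worst grade. The documents do not support that: it takes an overwrite before lock and a table built against SAP 6.9.

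A reader might also extend the point to adverse events of special interest. That fails. Protocol 7.1.1 says "Worsening of symptoms will be any new sign/symptom or shift in severity", and it makes the new or worsening sign the recorded event. It asks for a shift in grade, not a separate date of change.

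What the reply does not settle is an AE that began on study. Protocol 7.1 elsewhere refers to conditions present before study entry, so an on-study AE is not clearly pre-existing, and the wording in 5.8.1 is open. The DPC-only rule states an intention, but an undated worst grade gives no means of carrying it out.

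**Conclusion.** The point holds as a mismatch between what Protocol 7.1 lists for collection and what the OLE rule and SAP 6.9 require. As written, the second OLE criterion cannot be derived from the listed AE items. The consequences are possible rather than certain. An OLE worsening can be missed in the OLE tables; a later grade can enter the DPC table if the record is updated before core lock; and a grade reached after study drug was stopped can be shown as an on-treatment grade.

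The number of affected events cannot be estimated from the documents, which give no rate for AEs ongoing at Week 36 that later worsen. The 4-point figure is the effect of one patient in an arm of 25, not a forecast. The conclusion assumes that the eCRF follows the list in Protocol 7.1; a dated severity field in the eCRF would remove most of the problem. Safety analyses are descriptive, so the primary test and the secondary testing sequence are untouched. The point still merits a change, because a date not collected at the time may not be recoverable at analysis.

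**What to change.** - **Protocol 7.1 and the eCRF completion guideline:** state that any increase in the grade of an ongoing AE is captured with its date, either as a linked new record with its own start date and severity or as a dated severity entry on the existing record. Either convention works, provided one is chosen and applies to AEs that began on study.
- **SAP 6.9.2:** state that each period's intensity table uses the worst grade reached within that period's on-treatment window, so that DPC tables stop at the last blinded dose.

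The cost is one sentence in the protocol, one in the SAP, a guideline update and slightly more data entry at sites.

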**Table 1 Definition of Adverse Events Severity**

| INTENSITY | DEFINITION  |
|-----------|---|
| MILD      | A mild adverse event is one where the symptoms are barely noticeable to the patient. It does not influence the performance or prevent the patient from carrying on with normal life activities.   |
| MODERATE  | A moderate adverse event is one where the symptoms make a patient uncomfortable and cause some impairment to normal life activities. Treatment for symptom(s) may be required.  |
| SEVERE    | A severe adverse event is one where the symptoms cause severe discomfort to the patient and severely limit the patient's normal daily activities. Treatment for symptom(s) is given. Note that serious and severe are not synonymous. A serious adverse event must fulfill the requirements listed in the Section 7.2 . |

The Investigator will document in his/her opinion the relationship of the AE to the study medication using the criteria outlined in [Table 2](#). Causality assessment will be done for each of the IMP assessed in the study (octreotide capsules or placebo).

